**Piloting a Multi-component Technology-based Care Intervention to Address Patient Symptoms in Home Hospice**

NCT04243538

Protocol approved on 9/5/2024

**Research protocol** – a protocol is not a proposal but rather a description of the involvement of study subjects or study subject data, and how the study will be carried out; *as applicable*, the protocol should include:

- **Protocol Content** (*not all content areas will be applicable to every protocol*):
  - Purpose and **Specific Aims** of the study

The Specific Aims of the study are: (1) *To employ an iterative user-centered design process to develop I-HoME for home hospice patients and their caregivers (CGs)*, (2) *To conduct a single armed (N=10 CGs) pilot study with a focus on optimizing data collection protocols and the intervention before transitioning to*, (3) *To conduct a randomized pilot study evaluating the feasibility and potential efficacy of I-HoME (N=50 CGs) compared to usual care (N=50 CGs) and gather feedback on participants' experiences*, and (4) *To conduct a singled armed (N=6) pilot study delivering a modified version of the I-HoME intervention to assess feasibility*.

**Study design**, research methods, proposed intervention(s), rationale, hypotheses to be tested or issues to be addressed

This proposal seeks to develop and pilot test a multi-component technology-based care intervention, i.e., Improving **Home** hospice **M**anagement of **E**nd of life issues through technology (I-HoME), that focuses on assessing and addressing patient symptoms and caregiver (CG) burden in the home hospice setting. I-HoME will consist of two components: (1) synchronous live video interactions between CGs and a hospice nurse; and (2) educational videos. In Aim 1, I will develop the I-HoME protocol by incorporating best care practices and evidence-based management of patient symptoms and CG burden. Employing a user-centered design approach that incorporates family CGs and providers, the intervention will be refined and adapted for home hospice care. In Aim 2, I will conduct a single armed pilot study which will implement the intervention over 6 weeks and collect data to further optimize and refine the study and intervention protocols. Lastly, in Aim 3, I will evaluate the feasibility and potential efficacy of I-HoME in the home hospice setting, by comparing it to usual care.

### **Aim 1: I-HoME Protocol and Intervention Development**

**Synchronous Live Video – Patient Symptoms.** The patient symptom component of I-HoME will consist of weekly standardized assessment and management of signs/symptoms (e.g., pain, dyspnea, nausea, vomiting, agitation) experienced by the home hospice patient. In addition, visits on an as-needed basis (based on participant feedback and budget) can be requested by the patient, CG, and/or nurse interventionist, which may focus on a particular symptom or need. Development of the I-HoME protocol will focus on effectively evaluating and treating these symptoms along with other EoL symptoms through standardized assessments and management that incorporate education, non-pharmacologic and pharmacological therapies, and optimal use of hospice resources (e.g., respite, inpatient hospice care, etc.). A prototype intervention and manual of operations will be developed to incorporate existing best care practices and evidence-based research.

Doxy.me is a platform that will be used to conduct synchronous live video interactions between hospice nurses and patients/caregivers. Doxy.me is a secure and HIPAA compliant service. A business associate agreement will be obtained with Doxy.me prior to starting the study.

**Synchronous Live Video – CG Burden.** The CG component of I-HoME will focus on a weekly, standardized assessment and management of burden experienced by the CG. In addition, visits on an as-needed basis (based on participant feedback and budget) can be requested by the CG and/or nurse interventionist, which may address a particular type of burden. Development of the I-HoME protocol will focus on effectively evaluating CG burden and addressing it through education, skill building, coping strategy development, and optimal use of hospice resources (e.g., social work/spiritual care visit, respite, inpatient hospice care, etc.). A prototype intervention and manual of operations will be developed to incorporate existing best care practices and evidence-based research. Doxy.me is a platform that will be used to conduct synchronous live video interactions between hospice nurses and patients/caregivers. Doxy.me is a secure and HIPAA compliant service. A business associate agreement will be obtained with Doxy.me prior to starting the project/intervention.

**Educational Videos.** We will develop and use existing educational videos on patient symptoms and CG burden that reinforce the core principles delivered as part of the synchronous live video intervention. Videos will be developed and focus on topics around (but not limited to): 1) *assessing symptoms*, 2) *understanding medications in the emergency medicine kit*, 3) *what to do when symptoms escalate*, 4) *the importance of recognizing and addressing CG burden*, and 5) *an overview of hospice resources for family CGs*. Content for the videos will be based on existing best care practices and evidence-based research (literature review). We will receive feedback on the videos from patients, CGs, and hospice providers through our user-centered design protocol (see below). The revised educational videos will be shared based on the discretion of the hospice nurse interventionist during the intervention phase (Aims 2 and 3). Additional video topics may be developed depending on the needs of the hospice providers and/or patients/CGs.

**User-centered Design.** After the initial prototype development of I-HoME, an iterative user-centered design process will be employed to refine the intervention. Feedback and performance data from individuals who will interact with a prototype of the intervention will be gathered. Ten home hospice providers (e.g., nurses, nurse practitioners, physicians) along with ten home hospice patients and ten family CGs will be interviewed individually and recruited from the Visiting Nurse Service of New York (VNSNY). Participants will be

compensated with a \$50 gift card. Data collected during this process is outlined in **Appendix A**. Further details regarding recruitment, participant inclusion/exclusion criteria and informed consent forms are detailed in other sections of this protocol.

### **Aim 2: I-HoME single armed pilot study**

The aim of the single armed pilot study will be to optimize the proposed intervention and the data collection protocols while addressing any challenges that arise during initial implementation of the project. I will recruit 10 CGs (10% of the proposed recruitment planned for the pilot RCT in Aim 3) and implement the I-HoME intervention for up to a 6-week period (the period of intervention for each CG will be dependent upon the patient's length of stay on home hospice). Based on the data gathered from the single armed pilot study (see **Appendix B** and **Table 1** for data collection materials), I will modify the data collection protocols and intervention prior to moving on and conducting the pilot RCT.

**Intervention.** CGs will have access to video visits with a research nurse interventionist on a scheduled (weekly) basis. The study team will either make an in-home visit or conduct a phone call with the CG (based on CG preference) at the start of the study to obtain consent and train the CG on the I-HoME intervention. Participants who we obtain written consent from will be seen in-person and provided with a tablet equipped with cellular data connectivity. Participants who we obtain oral consent from will be mailed a tablet equipped with cellular data connectivity. Participants will also be given a laminated user guide/help card and have access to technical assistance if hardware or software concerns arise or if an adverse event occurs. Software by Doxy.me will be used to conduct HIPAA compliant synchronous video visits. Phone visits will be conducted if video visits are unable to be done due to hardware or software issues.

**Measurements.** All participants will be assessed on the measures listed in Table 1 (see **Appendix B** for more details). Measures will be administered at baseline and in weeks 1, 2, 3, 4, 5 and 6. Baseline measures will be collected during the in-home/virtual visit by the research team and subsequent measures will be collected via phone call. Post-visit measures will be collected during each interview, and additional measurements will be collected during the final interview. Participants will be compensated \$50 for an initial visit followed by \$25 (by ClinCard) each time they complete a within study, and post-intervention survey phone call/electronic survey. Data collected in Aim 2 will allow identification of study design issues that may not arise in Aim 1 and will provide opportunity to make refinements to the intervention before proceeding with the full pilot RTC study (Aim 3).

Table 1.

Baseline measures		Post-visit measures
Patient (from medical chart)	Caregiver	Caregiver
Age	Age	Burden
Gender	Gender	Depression
Race/ethnicity	Race/ethnicity	Anxiety
Religion	Religion	Software issues
Education	Education	Hardware issues
Comorbidities	Relationship to patient	Patient symptoms if patient cannot answer
Hospice diagnosis	Hours providing care to patient	CaSES
DNI/DNR status	Number of CGs caring for the patient	Caregiver (Final Interview)
Medications	Occupation	CG Satisfaction
Income	Income	Feasibility questionnaire

### **Aim 3: I-HoME pilot RCT**

For Aim 3, 100 CGs will be recruited from VNS Health hospice teams. The intervention will be randomized by nurse. Therefore, CGs of certain nurses will receive the I-HoME intervention (n=50) for up to six weeks while others will be recruited to receive standard home hospice care (n=50). Feasibility and potential efficacy measures will be administered at baseline and after each visit/weekly (timeline may change based on results obtained from Aim 2). Baseline measures will be collected during the in-home visit or via phone call by the research team and subsequent measures will be collected via phone call or electronic survey.

**Intervention.** CGs randomized to the intervention group will have access to live synchronous video visits with a research nurse interventionist on a scheduled (weekly) and as-needed basis (hours will be dependent on funding). The study team will either make an in-home visit or conduct a phone call with the CG (based on CG preference) at the start of the study to obtain consent and train the CG on the I-HoME intervention. This group will be educated about I-HoME and learn how to use the tablet to access videos and communicate with the interventionist. Participants will also be given a laminated user guide/help card and have access to technical assistance if hardware or software concerns arise or if an adverse event occurs. Software by Doxy.me will be used to conduct HIPAA compliant synchronous video visits. Participants in this study will continue to receive standard home hospice care in addition to the I-HoME intervention. Phone visits will be conducted if video visits are unable to be done due to hardware or software issues.

**Standard Care Control.** Participants in the standard care control group will receive home hospice services as usual. They will also receive a tablet with hospice resources. These participants will complete the same measures as participants in the intervention condition on the same timeline using identical assessment procedures.

**Measurements.** All participants will be assessed on the measures listed in Table 2 (see **Appendix B** for more details). Measures will be administered at baseline and in weeks 1, 2, 3, 4, 5 and 6. Validated surveys will be administered via phone by a research assistant. Post-visit measures for caregivers will be collected during each interview, and additional measures will be collected during the final interview. Participants will be compensated \$50 for an initial baseline survey followed by \$25 (by ClinCard) each time they complete a within study phone call/electronic survey. Post-intervention measures for patients will be collected from their medical chart in both groups. For the intervention group, the collection will start from study enrollment to 4 weeks after the final I-HoME intervention visit or the date of program end (which ever one is earlier). For the control group, the collection will start from study enrollment to 11 weeks after enrollment.

Table 2.

Baseline measures		Post-intervention measures	
Patient (from medical chart)	Caregiver	Caregiver	Patient
Age	Age	Burden	Hospice discharge reason
Gender	Gender	Depression	Use of non-home hospice services (inpatient care, respite care)
Race/ethnicity	Race/ethnicity	Anxiety	Number of nursing visits
DNI/DNR status	Religion	Software issues	Number of social work visits
Medications	Education	Hardware issues	Number of chaplain visits
Comorbidities	Relationship to patient	Patient symptoms	
Hospice diagnosis	Hours providing care to patient	CaSES	
	Number of CGs caring for the patient	Caregiver (Final Interview)	
	Occupation	CG Satisfaction	
	Income	Feasibility questionnaire	

### Addition of patient participants for Aim 3

We will pilot patient participants (n=20) to answer a survey about their symptoms at baseline, 2 weeks, 4 weeks, and 6-weeks. The survey is the Edmonton Symptoms Assessment Scale (ESAS) which takes approximately 5 minutes to complete. We will also clarify to the patients that the ESAS data collected will not be shared with the clinical team and is for research purposes only. Enrollment of patients will help us understand the feasibility of interviewing hospice patients, and we will also analyze the differences in the ESAS scores from the dyad of caregiver and patient. Participants will be compensated a total of \$50 for their participation. The gift card will be mailed after they have given oral consent and completed the baseline survey questions over the phone. We are suggesting an alteration of written consent and the use of oral consent. The patients are in hospice care and will likely find in-person visits or other forms of written or electronic consents to be burdensome. Their participation involves no more than minimal risks to the subjects, and the oral consent

obtained over the phone will not adversely affect the rights and welfare of subjects. Whenever appropriate, subjects will be provided with additional pertinent information after participation.

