### **Addition of exit interviews for Aim 3**

We will ask caregivers who participated in the Aim 3 randomized pilot study, nurses of these caregivers' care recipients, and the nurse practitioner interventionists who conducted the telehealth visits to complete a recorded phone interview asking about their experiences with the I-HoME program. The interview will take approximately 30-45 minutes for the caregivers, 10-15 minutes for the nurses, and 30 minutes for the interventionists. The interviews will be transcribed and anonymized to destroy any identifying information upon transcription. The questions asked are listed in Interview – Aim 3 documents below. The in-depth qualitative interviews will help us understand the feasibility and acceptability of the I-HoME intervention and ways to modify the intervention to make it more helpful for caregivers. Participants will be compensated \$50 for their participation. The gift card will be mailed after they have given oral consent and completed the phone interview. The oral consent obtained over the phone will be less burdensome than other forms of written or electronic consents. The participation involves no more than minimal risks to the subjects, and the oral consent obtained over the phone will not adversely affect the rights and welfare of subjects.

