### **Aim 4: Modified I-HoME single armed pilot study**

The aim of the single-armed pilot study will be to examine the feasibility of providing I-HoME over the course of 3-weeks. This would include 2 tele-visits per week for up to 3 weeks instead of Aim's 3 weekly televisit over the course of 6 weeks. Our rationale for pilot testing this is to address the attrition concerns encountered in the existing data collected. While we found administering the tele-visits feasible, we also noticed that many caregivers didn't complete the six-week intervention (this was mainly because their loved one passed away earlier, so they didn't get the full benefit of the 6 visits). In Aim 4, we will pilot test a 3-week program, delivering 6 televisits, and examine its feasibility.

**Intervention.** A nurse practitioner interventionist will deliver the I-HoME intervention through a televisit twice a week for up to 3 weeks. The study team will conduct a phone call with the CG at the start of the study to obtain verbal consent and train the CG on accessing the televisit platform. Participants will also be mailed a user guide and have access to technical assistance if software concerns arise or if an adverse event occurs. Software by Doxy.me will be used to conduct HIPAA compliant synchronous video visits. Phone visits will be conducted if video visits are unable to be done due to hardware or software issues.

**Measurements.** All participants will be assessed on the measures listed in Table 3. Baseline CG demographic data will be collected during after consent and an exit interview will be conducted by phone when the participant completes the study. Participants will be compensated \$50 for the initial survey, and \$50 for the exit interview.

Table 3. Study measures for Aim 4

Caregiver
Age
Gender
Race/ethnicity
Religion
Education
Relationship to patient
Hours providing care to patient
Number of CGs caring for the patient
Occupation
Income

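### Aim 3 patient chart outcomes are collected over a fixed 11 weeks in control but over a window set by the last I-HoME visit, or an undefined 'program end', in the intervention arm

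*Combined protocol and SAP*

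**What the plan says.** Aim 3, Measurements, sets the collection period for the patient outcomes in Table 2: hospice discharge reason, inpatient and respite use, and numbers of nursing, social work and chaplain visits.

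- Control: "For the control group, the collection will start from study enrollment to 11 weeks after enrollment".
- Intervention: "the collection will start from study enrollment to 4 weeks after the final I-HoME intervention visit or the date of program end", whichever is earlier.

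The text that bears on the intervention window is:

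- Caregivers of certain nurses "will receive the I-HoME intervention (n=50) for up to six weeks", with visits "on a scheduled (weekly) and as-needed basis".
- Aim 4 looks back on Aim 3 as a six-visit course. It reports that many caregivers did not finish and so did not "get the full benefit of the 6 visits"; "this was mainly because their loved one passed away earlier".
- 'Program end' has no definition. The exit-interview section uses the word for I-HoME itself ("asking about their experiences with the I-HoME program"), and so does Aim 4 ("we will pilot test a 3-week program, delivering 6 televisits"). The data and safety monitoring plan (DSMP), Brief Description of Project Design, speaks instead of twelve weeks. It also times post-intervention measures at 4 weeks after death, without saying whether chart data are meant.

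The DSMP's Specific Aims list live hospice discharge among the efficacy outcomes. The Brief overview of analytic methods plans mixed models and gives no exposure offset, rate or common truncation for chart outcomes.

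**The concern.** All of these outcomes accumulate with observation time. The control window is fixed at enrolment. The intervention window depends on when the last visit happens, which moves with the delay to the first visit, with as-needed visits and with early stopping. An intervention caregiver who never has a visit has no anchor except the undefined 'program end'.

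If raw counts or proportions are compared, the arms can differ because one was watched longer. Live discharge is the clearest case, since it is a named efficacy outcome and discharge reason is read from the chart through this window. Respite and inpatient use also matter, because Aim 1 makes good use of those hospice resources part of what the intervention teaches. The plan does not say that the nursing, social work or chaplain counts will be tested.

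**Working it through.** **Inputs from the plan.** Control window 11 weeks; intervention window = last visit + 4 weeks; six weekly visits (Aim 4's description of Aim 3); mortality 35%, 62% and 72% at 4, 8 and 12 weeks (power paragraph).

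**Assumptions.** Mortality is the same in both arms and counted from enrolment. Survival is linear between the stated points: S(0) = 1, S(4) = 0.65, S(8) = 0.38, S(12) = 0.28. The plan does not derive the 11 weeks, so there is no figure of its own to reproduce.

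**When do the windows match?** Last visit + 4 = 11 gives a last visit at week 7. Six weekly visits span 5 weeks, so the first must fall 2 weeks after enrolment. That delay is not stated.

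**Person-time.** Mean weeks alive in a window of W weeks is the area under S from 0 to W. For example, 0–4 weeks gives 4 × (1 + 0.65)/2 = 3.300. Adding week 5 gives 3.300 + (0.65 + 0.5825)/2 = 3.916. Continuing:

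| W (weeks) | 5 | 6 | 7 | 8 | 9 | 10 | 11 | 12 |
|---|---|---|---|---|---|---|---|---|
| Mean weeks alive | 3.916 | 4.465 | 4.946 | 5.360 | 5.728 | 6.070 | 6.388 | 6.680 |

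With every surviving patient's caregiver completing six visits:

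| First visit (week) | Last visit (week) | Intervention window (weeks) | Control / intervention person-time |
|---|---|---|---|
| 0 | 5 | 9 | 6.388/5.728 = 1.115 |
| 1 | 6 | 10 | 6.388/6.070 = 1.052 |
| 2 | 7 | 11 | 1.000 |
| 3 | 8 | 12 | 6.388/6.680 = 0.956 |
| 'Program end' at week 6 | – | 6 | 6.388/4.465 = 1.431 |

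**Early stopping with the patient alive.** Suppose a fraction p stop, with last visits spread evenly over weeks 1–5. Their windows are 5–9 weeks, with mean area (3.916 + 4.465 + 4.946 + 5.360 + 5.728)/5 = 4.883. Intervention person-time is then (1 − p) × area for the others + p × 4.883. For p = 0.1 and the others ending at week 6: 0.9 × 6.070 + 0.1 × 4.883 = 5.951, and 6.388/5.951 = 1.073. For p = 0.1, 0.2 and 0.3 the ratios are:

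- others end at week 6: 1.073, 1.095, 1.118
- others end at week 7: 1.024, 1.049, 1.076

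**Sensitivity to the model.** A piecewise-exponential curve through the same points gives control 6.28 weeks and an intervention/control ratio of 0.95 for a last visit at week 6. In a simulation with that curve and visits at weeks 1–6, stopping probabilities of 5%, 10% and 20% per week unrelated to death gave ratios of 0.91, 0.87 and 0.80. These are heavy assumptions: without any deaths, 1 − 0.95⁵ = 23%, 1 − 0.90⁵ = 41% and 1 − 0.80⁵ = 67% would miss the sixth visit.

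**False-positive rate on raw counts.** Simulation of 10,000 trials per scenario, 50 per arm, no true effect, t-test at nominal 5%, 1–3 visits per week (assumed), nurse clustering ignored. The last column adds gamma variation between patients in visit rate (coefficient of variation 0.5 or 1, assumed).

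| Intervention window (weeks) | Poisson counts | With between-patient variation |
|---|---|---|
| 11 | 5% | 5% |
| 10 | 6–7% | 5–6% |
| 9 | 11–14% | 6–10% |
| 12 | 6–7% | 5–6% |
| 6 | 70–82% | 23–56% |

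**Live discharge.** Cumulative incidence is the integral of h·S(t)·exp(−ht), with h = 1%, 2%, 3% per week (assumed):

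- 11 weeks: 6.12%, 11.73%, 16.88%
- 10 weeks: 5.83%, 11.22%, 16.19% (0.3–0.7 points lower)
- 6 weeks: 4.35%, 8.47%, 12.38% (1.8–4.5 points lower)

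**The case against.** The case for leaving this alone is reasonable in several parts.

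- **The main-reading effect is small.** A 10- versus 11-week window moves live discharge by 0.3–0.7 points, about 0.15–0.35 of one patient among 50. At lower event rates, more typical of respite or inpatient use (0.05–0.25 per week, assumed), the false-positive rate is about 5–6% for a 10-week window and 6–8% for 9 weeks. This stands.
- **Poisson counts overstate the error rate.** This also stands, and the last column of the false-positive table shows by how much.
- **Death removes much of the asymmetry.** When visits stop because the patient dies, the 4-week tail normally runs past the death and the chart is complete in both arms. This stands. What remains is stopping with the patient alive, whose frequency is not given.
- **The large figures need an implausible reading.** If 'program end' meant week 6, the 4-week tail in the same sentence would have almost no effect. If it meant the end of hospice enrolment, the clause would create little asymmetry. Either way the reader has to guess.
- **Eleven weeks may have been chosen to match** a start-up delay plus six weeks plus four. That is possible but not stated, and it holds only for a last visit at week 7.
- **Feasibility is the primary aim, and the appendices are not in the text available.** The first limits the harm. On the second, dated events may already be recorded; Table 2 lists only numbers of visits.

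None of this makes the two rules equivalent. Carried out as written, they give unequal ascertainment by arm.

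**Conclusion.** The concern holds. The chart window differs by arm, the intervention window depends on a post-allocation event and an undefined term, and no stated analysis rule corrects for it.

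The likely size is modest. With six weekly visits, control has between 12% more and 4% less person-time. If 10–30% stop early with the patient alive and the others end at week 6 or 7, control has 2–12% more. Heavier stopping would widen this. The 43% gap applies only if 'program end' is week 6, and should carry little weight. These figures rest on the plan's mortality, equal survival in the arms, and assumed start delays, stopping patterns and event rates, so neither size nor direction can be read from the plan.

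The harm is confined to secondary utilisation and discharge comparisons. Feasibility endpoints and weekly caregiver outcomes are not touched. It should still be fixed, because the bias is avoidable and the repair is cheap.

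**What to change.** 1. Use one chart window in both arms, counted from enrolment, independent of visit attendance, and ended the same way by death or hospice discharge. It could be 11 weeks for everyone, or both arms truncated at the same week at analysis.
2. Abstract event dates. Undated visit totals cannot be truncated later.
3. Define 'program end' or remove it.
4. Report counts per person-time on hospice, for example with a log person-time offset.
5. State whether the DSMP's timing of 4 weeks after death applies to chart data.

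The window change is one sentence in the protocol and needs no patient contact, since charts are already to be reviewed at the end of the study. The cost is a few more weeks of abstraction for some intervention patients and re-review of any charts already abstracted (Aim 4 refers to existing data). If both arms are truncated, some control follow-up is discarded instead.
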